PR	Partial Response
QOL	Quality of Life
RAD001	Everolimus
RANKL	Receptor activator of nuclear factor kappa B ligand
RECIST	Response Evaluation Criteria In Solid Tumors
SAE	Serious Adverse Event
SAR	Suspected Adverse Reaction
SD	Stable Disease
SGPT	Serum Glutamic-Pyruvic Transaminase

SPC	Summary of Product Characteristics
SUSAR	Suspected Unexpected Serious Adverse Reaction
TK	Tyrosine Kinase
TNBC	Triple negative breast cancer
TTP	Time To Progression
YOB	Year of Birth

EUDRACT-NO.: 2013-001269-18	Protocol No.: D-IV
Sponsor: Universitätsklinikum Ulm (AöR), [name], [name]	
Responsible person: [name]. [name], University Hospital Ulm	
Coordinating Investigator („Leiterin der klinischen Prüfung“ acc. to German Drug Law): [name]. [name], University Hospital Düsseldorf	
Title: DETECT IV – A prospective, multicenter, open-label, phase II study in patients with HER2-negative metastatic breast cancer and persisting HER2-negative circulating tumor cells (CTCs).	
Investigational medicinal products (IMP): DIVa: Everolimus tablets 5 mg/Ribociclib capsules 3 x 200 mg /d d 1-21 q28d or DIVb: Eribulin mesylate 1.23 mg/m² d1+8 q3w	
Indication/Clinical Trial population	

Everolimus/Ribociclib cohort: Postmenopausal female patients with hormone-receptor positive, HER2-negative metastatic breast cancer with only HER2-negative circulating tumor cells (CTCs) and indication for standard endocrine therapy.
	

Eribulin cohort: Patients with hormone-receptor positive, HER2-negative metastatic breast cancer and indication to chemotherapy or patients with triple-negative metastatic breast cancer, both with only HER2-negative circulating tumor cells (CTCs).
	

Clinical Trial Design

A prospective, multicenter, open-label, phase II study.

[figure not shown]

Figure 1: Screening and Design of DETECT IV

Planned duration of the entire study

The study starts when the necessary approval has been given by the competent authority (BfArM). Furthermore the competent ethics committee must have given a favorable opinion on study conduct before the first patient is included.

The trial is terminated after the last patient has either died or completed the 24-months follow-up period.

The maximum study duration is 72 months and 3 weeks.

Planned duration of individual study participation

The individual study participation begins with the screening visit and ends when the patient has either died or completed the 24-months follow-up period.

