4.3 Schedule

The individual study participation begins with the screening visit, consists of endocrine therapy plus everolimus/ribociclib or therapy with eribulin (depending on the treatment cohort) and ends with disease progression, the patient's death or with completion of the follow-up period. The estimated maximum duration of individual study participation is 36 months and 3 weeks both for the everolimus/ribociclib cohort and the eribulin cohort.

Patient participation is divided in 3 consecutive periods:

Pre-Treatment Evaluation Period:

Content:	Examinations and collection of data relevant to decide on patients' eligibility for further study participation. Informed consent 1
Period:	From screening to inclusion
Maximum duration:	3 weeks
Visits:	From Screening Visit to end of Inclusion Visit

Treatment Period:

Content:	Endocrine therapy combined with everolimus/ribociclib or chemotherapy with eribulin.
----------	--

Assessment of efficacy and safety data.
Informed consent 2 and 3

Period: From inclusion until disease progression or occurrence of other criteria for treatment discontinuation

Maximum duration: 12 months* (both for the everolimus/ribociclib cohort and the eribulin cohort) or until progress / death or discontinuation due to toxicities or other reasons

Visits: From Inclusion Visit to Conclusion Visit (4 weeks after last application of everolimus/eribulin)

*After treatment period the treatment with everolimus/ribociclib or eribulin can be extended if medically indicated. Patients will be followed up for toxicity and efficacy in such cases. The drug will be supplied by Novartis (everolimus/ribociclib), respectively Eisai (eribulin) on study terms for the duration of the individual study participation (including 2-year-period of follow-up assessments).

Follow-Up period:

[figure not shown]
Content: Assessment of survival, adverse events and concomitant medication. Treatment of the metastatic disease at the investigator's discretion

Period: From end of study treatment until the patient has either died or completed the 24-months follow-up period

Maximum duration: 24 months (estimation)

Visits: From Conclusion Visit of the Treatment Period to the last Follow-Up Visit

Figure 9: Clinical Trial Design

Entire Study:

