Patients who interrupt everolimus therapy for more than 4 weeks must be discontinued from the study.

TABLE 15 and TABLE 16 provide the procedure to be followed for everolimus dose modification in the event of toxicities suspected to be related to the everolimus treatment. Included are also instructions for re-initiation of everolimus dosing once sufficient recovery of toxicity is seen.

Toxicity	Actions
Metabolic events (e.g. Hyperglycemia, Hyperlipidemia and/or hypertriglyceridemia)	
Grade 1: No dose adjustment required. Initiate an appropriate medical therapy and monitor.
 
Grade 2: No dose adjustment required. Initiate an appropriate medical therapy and monitor.
 
Grade 3: Interrupt everolimus until recovery to grade ≤ 1. Reintroduce everolimus at the next lower dose level. . Initiate an appropriate medical therapy and monitor
 
Grade 4: Discontinue everolimus treatment

Stomatitis	
Grade 1: No dose adjustment required.
 
Grade 2: Interrupt everolimus until resolution to \leq grade 1. Restart at the same dose. If stomatitis recurs at grade 2, interrupt dose until recovery to grade ≤ 1. Restart at a lower dose.
 
Grade 3: Interrupt everolimus until recovery to grade ≤ 1. Reintroduce everolimus at the next lower dose level
 
Grade 4: Discontinue everolimus treatment

Pneumonitis	
Grade 1: No dose adjustment required. Initiate appropriate monitoring.
 
Grade 2: Consider interruption of therapy, rule out infection and consider treatment with corticosteroids until symptoms resolve to \leq grade 1. Restart at a lower dose. Discontinue treatment if failure to recover within 4 weeks.
 
Grade 3: Discontinue everolimus, rule out infection and consider treatment with corticosteroids until symptoms resolve to \leq grade 1. Consider restart at a lower dose level. Discontinue treatment if failure to recover within 4 weeks.
 
Grade 4: Discontinue everolimus treatment rule out infection and consider treatment with corticosteroids.

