8.3.2.1 Permitted study drug dose adjustments and interruptions

For patients who are unable to tolerate the protocol-specified dosing scheme, dose adjustments and interruptions are permitted in order to keep the patient on the study drugs. The following guidelines should be followed.

These changes must be recorded on the Dosage Administration Record eCRF.

Treatment with ribociclib and standard endocrine therapy should continue as long as clinical benefit is observed or until unacceptable toxicity occurs. Management of severe and/or intolerable suspected adverse events may require temporary dose reduction and/or interruption.

For patients who do not tolerate the protocol-specified ribociclib dosing schedule, dose adjustments are permitted in order to allow the patient to continue the study. The following guidelines need to be applied:

All study drug interruptions or dose modifications must be recorded on the Dosage Administration Record page of the eCRF.

	Dose	Number of tablets & strength
Starting dose	600 mg/d	3 x 200 mg tablets
First Dose reduction	400 mg/d	2 x 200 mg tablets
Second dose reduction	200 mg/d	1 x 200 mg tablets

Table 19: Ribociclib Dose Modification guidelines

If a patient has already decreased ribociclib intake to 200 mg every other day, no further dose reduction is permitted. Patients requiring an additional ribociclib dose reduction will be required to discontinue study treatment.

Patients who interrupt ribociclib therapy for more than 4 weeks must be discontinued from the study.

TABLE 20, TABLE 21, TABLE 22 and TABLE 23 provide the procedure to be followed for ribociclib dose modification in the event of toxicities suspected to be related to the ribociclib treatment. Included are also instructions for re-initiation of ribociclib dosing once sufficient recovery of toxicity is seen.

Toxicity	Actions
HEPATOTOXICITY (BILIRUBIN; SGPT/ALT, SGOT/AST)	

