8.4.2 Dose Adjustments

In General

Doses may be held or reduced for hematologic and other adverse events (see section 8.3.2.1). Dose adjustments are to be made according to the system showing the greatest degree of toxicity. Once dose is reduced due to adverse events, patients should not be re-challenged to a higher dose level.

Dose reductions and delays of treatment should follow general GCP criteria for the application of antineoplastic drugs (Repetto et al. 2003, NCCN-Guidelines) and should be made according to the SPC and/or investigator's brochure. The latest versions of the SPCs ("Fachinformation" according to German Drug Law) of the standard therapy will be provided on the DETECT IV website or by contact the DETECT Study Office in Ulm (Univeritäts-frauenklinik Ulm, Studienzentrale, [name], [name], [contact], [contact], Email: [contact]).

The antineoplastic treatment of a patient can be postponed for up to 4 weeks to allow resolution of toxicity. The investigator must consult the DETECT IV Study Office prior continuing therapy for any patient requiring a delay of study treatment of more than two weeks for any reason.

All patients who require permanent discontinuation of eribulin will be withdrawn from the treatment intervention schedule (start of the 2-year follow-up period).

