8.4.2.1 Permitted study drug dose adjustments and interruptions

Treatment with eribulin should continue as long as clinical benefit is observed or until unacceptable toxicity occurs. Management of severe and/or intolerable suspected adverse events may require temporary dose reduction and/or interruption.

For patients who do not tolerate the protocol-specified eribulin dosing schedule, dose adjustments are permitted in order to allow the patient to continue the study. The following guidelines need to be applied: Dose adjustments are permitted for any adverse event suspected to be related to eribulin in those patients unable to tolerate the normal dose. If administration of eribulin must be interrupted because of unacceptable toxicity, eribulin dosing will be interrupted or modified according to the guidelines in TABLE 15 below.

All study drug interruptions or dose modifications must be recorded on the Dosage Administration Record page of the eCRF.

For patients who are unable to tolerate the protocol-specified dosing scheme, dose adjustments and interruptions are permitted in order to keep the patient on the study drugs. The following guidelines should be followed.

The administration of eribulin should be delayed on Day 1 or Day 8 for any of the following:

- Absolute neutrophil count (ANC) < 1000/μl
- Platelets < 75000/μl
- Grade 3 or 4 non-hematological toxicities.

Patients who interrupt eribulin therapy for more than 4 weeks must be discontinued from the study.

Dose reduction during therapy

Dose reduction recommendations for retreatment are shown in the following TABLE 24.

Adverse reaction after previous eribulin administration	Recommended dose of eribulin
Haematological:	
ANC < 0.5 x 10 ⁹ /l lasting more than 7 days	0.97 mg/m²
ANC < 1 x 10 ⁹ /l neutropenia complicated by fever or infection	
Platelets < 25 x 10 ⁹ /l thrombocytopenia	
Platelets < 50 x 10 ⁹ /l thrombocytopenia complicated by haemorrhage or requiring blood or platelet transfusion	
Non-haematological:	
Any Grade 3 or 4 in the previous cycle	
Reoccurrence of any haematological or non-haematological adverse reactions as specified above:	
Despite reduction to 0.97 mg/ m ²	0,62 mg/m²
Despite reduction to 0.62 mg/m ²	Consider discontinuation

Table 24: Eribulin dose modification guidelines for toxicities.

Do not re-escalate the eribulin dose after it has been reduced.

Patients with hepatic impairment

Impaired liver function due to metastases:

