13 TREATMENT DISCONTINUATION AND PREMATURE STUDY DISCONTINUATION

13.1 Protocol Treatment Discontinuation

13.1.1 Criteria for Discontinuing Protocol Treatment

Study drug discontinuation

Study drug interruption refers to a patient stopping either study drug during the course of the study, but then re-starting it at a later time in the study. If the study drug everolimus/ribociclib is interrupted for more than 4 weeks, the patient will be permanently discontinued from the study.

If the administration of study drug must be interrupted because of an unacceptable toxicity, dosing will be interrupted or modified according to rules described in TABLE 14, TABLE 15, TABLE 16, TABLE 17 for everolimus-cohort and TABLE 19, TABLE 20, TABLE 21, TABLE 22 and TABLE 23 for ribociclib-cohort. A patient who requires dose interruption (regardless of the reason for the interruption) lasting > 4 weeks (counting from the first day when a dose was missed) must discontinue study treatment. All study drug interruptions must be recorded on the appropriate Dosage Administration CRF.

Patients whose treatment is interrupted due to an adverse event or abnormal laboratory value must be followed at least once a week for 4 weeks and subsequently at 4 weeks intervals, until resolution or stabilization of the event, whichever comes first.

Study discontinuation refers to a patient's withdrawal from study drug. The reason for discontinuation from treatment must be recorded on the End of treatment CRF.

Patients who discontinue study drug > 4 weeks should be scheduled for an End of treatment Visit, as soon as possible, after discontinuing study drug, at which time all of the assessments listed for the End of treatment Visit will be performed. The complete End of treatment CRF documentation should be done within one week. The date and reason for stopping the study treatment should be recorded on the CRF.

Study drug will be discontinued for any of the following reasons:

- Tumor progression (as defined in section 10.2.)
- Toxicity/ Unacceptable adverse events
- Consent withdrawal/ Request by the patient
- Dose interruption of > 4 weeks
- Intercurrent illness that prevent further administration of study drug
- Need for any other types of anticancer therapy, except for palliative radiotherapy for bone lesions
- General or specific changes in the patient's condition which render the patient unacceptable for further treatment at the discretion of the investigator

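### Section 4.3 lists progression as an end of participation, and five places take patients off the study after a drug interruption of more than 4 weeks; both contradict the 24-month follow-up and, if applied literally, risk informative censoring of overall survival

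*Protocol*

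**What the plan says.** **End of participation.** Section 4.3 opens by describing participation as running from screening through treatment, "depending on the treatment cohort) and ends with disease progression", and then adds death and completed follow-up as the other endings. The synopsis (planned duration of individual study participation) names only the last two: participation "ends when the patient has either died or completed the 24-months follow-up period". Further down, section 4.3 ends the treatment period at progression and gives the follow-up period, whose content includes survival, as "From end of study treatment until the patient has either died or completed the 24-months follow-up period". The end-of-trial definition in 4.3 and the German synopsis in Appendix I agree with the synopsis.

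**Interruption of more than 4 weeks.** Three sections use the same wording for the three drugs:
- 8.2.2.1: "Patients who interrupt everolimus therapy for more than 4 weeks must be discontinued from the study"
- 8.3.2.1: "Patients who interrupt ribociclib therapy for more than 4 weeks must be discontinued from the study"
- 8.4.2.1: "Patients who interrupt eribulin therapy for more than 4 weeks must be discontinued from the study"

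Section 8.6.4 and one sentence of 13.1.1 say the same. Another sentence of 13.1.1 requires only that such a patient stop study treatment. Section 13.1.1 also states: "Study discontinuation refers to a patient's withdrawal from study drug".

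**Start of follow-up.** For eribulin, 8.4.2 says: "All patients who require permanent discontinuation of eribulin will be withdrawn from the treatment intervention schedule (start of the 2-year follow-up period". Sections 8.2.2 and 8.3.2 have a parallel sentence for everolimus and ribociclib, but it applies only when both the study drug and the endocrine agent are permanently stopped.

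**The concern.** The protocol gives sites incompatible instructions on when a patient's data collection ends. On the opening sentence of 4.3, a patient who progresses is finished, although progression is the event that should move her from treatment into follow-up. On the interruption wording, a patient whose drug is held for more than 4 weeks leaves the study altogether. Because 13.1.1 equates study discontinuation with coming off drug, section 13.1.1 has no separate term for leaving follow-up.

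Overall survival is a secondary endpoint in every cohort, and quality-adjusted survival by Q-TWiST depends on it. Under section 1.2.2, a patient not known to have died is censored at last contact. If contact ends because she progressed or had a long interruption, the censoring is related to prognosis. Kaplan-Meier then treats as non-informative something that is not, and the result would depend on which sentence each site followed. For the eribulin primary endpoint, PFS, the exposure is narrower: it concerns only patients taken off the study before progression.

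**Working it through.** **1. The plan's own figures.**
- Maximum participation: 3 weeks + 12 months + 24 months = 36 months and 3 weeks, as stated. The sum includes the follow-up period but does not settle who enters it.
- Eribulin precision (section 15.3): median PFS 3.7 months, n = 108, all taken as events, exponential times. Width of the 95% interval = 3.7 × (exp(1.96/√108) − exp(−1.96/√108)) = 1.40 months, inside the stated 1.3–1.5. The exponential assumption below is therefore consistent with the plan's own calculation.

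**2. The texts side by side.**

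| Question | Takes the patient off | Keeps her in follow-up |
|---|---|---|
| Progression | 4.3, opening sentence | 4.3 follow-up block and end-of-trial definition; synopsis; 9.1 (conclusion visit at progression, with a reminder about follow-up); 9.2 (survival at least every three months); 13.1.3; Appendix II |
| Interruption > 4 weeks | 8.2.2.1, 8.3.2.1, 8.4.2.1, 8.6.4, one sentence of 13.1.1 | another sentence of 13.1.1 (treatment only); 8.4.2; 8.2.2 and 8.3.2 if both agents are stopped |
| Reasons for premature end of participation | – | 13.2 names neither progression nor interruption |

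DIVa has an additional gap. The 4-week rule is triggered by everolimus or ribociclib alone, whereas the follow-up sentence in 8.2.2 and 8.3.2 needs both agents to be stopped. A patient who stops only everolimus or ribociclib meets the first rule and not the second.

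**3. Patients reaching a PFS event during treatment.** Share by month 12 = 1 − 2^(−12/median).
- Eribulin, 3.7 months (15.3): 0.894, or 96.6 of 108.
- Triple-negative patients on eribulin, 2.9 months (2.7.3): 0.943.
- Everolimus plus exemestane, 7.8 months (2.7.1): 0.656.

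**4. Deaths with follow-up as intended.** Eribulin median OS is 13.1 months (2.7.3). Deaths = 108 × (1 − 2^(−t/13.1)).
- t = 24 months: 77.7.
- t = 36 months: 91.9.

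**5. Deaths if participation stopped at progression.** Only deaths that are themselves the first PFS event would be seen. The documents do not give that share, s, so a range of 5–20% is assumed. Deaths = 108 × s × (1 − 2^(−36/3.7)). The apparent OS median is 3.7/s, because the observed death hazard is s times the PFS hazard.

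| s (assumed) | Deaths seen of 108 | Apparent OS median (months) |
|---|---|---|
| 5% | 5.4 | 74.0 |
| 10% | 10.8 | 37.0 |
| 20% | 21.6 | 18.5 |

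For 5% and 10% the apparent median lies beyond 36 months, so the curve would not be expected to reach it.

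**6. Interruption wording.** The protocol gives no rate of interruptions longer than 4 weeks, so no count can be derived.

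**The case against.** The strongest reply is that the operational text already requires the data. Section 9.1 calls the conclusion visit at progression or other premature discontinuation. Section 9.2 then collects survival by visit or telephone. Appendix II shows the same sequence, and 13.1.3 describes the follow-up period for patients who stopped early as well as for those who completed treatment. Section 13.2 lists only patient request, jeopardy as judged by the investigator, and pregnancy. Reading 13.1.1 with its own definition, leaving the study after a long interruption can be taken to mean coming off drug. Section 8.6.2 also requires a final progression and survival update for every patient.

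Most of this stands. It shows the likely intent and makes the interruption part largely a matter of terminology. A reader might infer from the literal wording that survival after progression will not be collected and that OS will be biased. The documents do not support that as a statement of fact.

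The reply does not remove the contradiction in the opening sentence of 4.3, which the definition in 13.1.1 does not touch. Nor does it cover the DIVa patient who stops one agent. The final update helps only in part: it is a single late contact, and 13.1.1 places it after the last patient's last dose while 8.6.2 places it at study end. A patient whose file was closed and who cannot be reached later stays censored early.

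Two stronger figures are also tempting. One could take the cited treatment discontinuations (5 of 54 with tamoxifen plus everolimus, 4% with eribulin for neuropathy) as the number lost to the interruption rule. Those are discontinuations of treatment, not interruptions over 4 weeks, and for eribulin 8.4.2 sends permanent discontinuations into follow-up. One could also compute (13.1 − 3.7)/13.1 = 72% as the share of survival time after progression. That compares two medians and is at most indicative.

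**Conclusion.** The contradictions are established from the text, both within section 4.3 and between the interruption wording and the follow-up provisions. The consequence is conditional: a site following the literal sentences could close patients early and censor OS, and hence Q-TWiST, in a way related to prognosis.

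The size under the literal 4.3 sentence is about 5–22 observed deaths in 108 eribulin patients, against about 78–92 with follow-up as intended. This is a worst case with every site applying that sentence. It rests on exponential times, on the medians cited in the protocol, and on an assumed 5–20% share of deaths among first PFS events. The interruption part has no supportable number. The primary eribulin PFS is touched only for patients taken off the study before progression. This is worth correcting because the remedy is cheap; it is not evidence that the survival data will be lost.

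**What to change.** 1. In the opening sentence of 4.3, delete progression as an end of individual participation, leaving death or completed follow-up as in the synopsis.
2. Reconcile the interruption wording in 8.2.2.1, 8.3.2.1, 8.4.2.1, 8.6.4 and 13.1.1 with the sentence in 13.1.1 that refers to treatment only. State that these patients continue in the section 9.2 follow-up, including DIVa patients who stop only everolimus or ribociclib.
3. In 13.1.1, define stopping study drug separately from ending study participation, and let 13.2 govern the latter. A new closed list limited to consent withdrawal, loss to follow-up and death would conflict with 13.2 and with the pregnancy rule in section 12.

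The treatment rules themselves, including the 4-week limit, are for the sponsor; no view on them is needed here. The cost is amendment wording. Section 9.2 already plans the follow-up contacts, so no new procedure is added; the protocol does not show how they are funded.
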